### **6.8.3. Concomitant Medications for Conditions Other Than Psoriasis**

Every effort should be made to keep participants on stable concomitant medications. If the medication is temporarily discontinued because of abnormal laboratory values, side effects, concurrent illness, or the performance of a procedure, the change and reason for it should be clearly documented in the participant's medical record.

The use of stable doses of nonsteroidal anti-inflammatory drugs is allowed. However, disease-modifying agents such as MTX, sulfasalazine, or IM gold are prohibited during the study.

The use of corticosteroids for indications other than psoriasis should be limited to situations for which, in the opinion of the treating physician, there are no adequate alternatives. They should be used on a short-term basis, preferably for  $\leq 2$  weeks. Longer-term use of corticosteroids should be discussed with the medical monitor or designee and may require discontinuation of study drug. Inhaled, otic, ocular, nasal, or other routes of mucosal delivery of corticosteroids are allowed throughout the study.

The Sponsor must be notified in advance (or as soon as possible thereafter) of any instances in which prohibited therapies are administered.

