5. STATISTICAL ANALYSES

5.1. General Considerations

In general, descriptive statistics will include counts and percentages for categorical variables, and mean, standard deviation (SD), median, interquartile (IQ) range, minimum, and maximum for continuous variables. Graphical data displays may also be used to summarize the data.

In this study, efficacy will be evaluated through Week 48. In addition, PK, immunogenicity, PD, biomarker, and safety measurement, and selected participant information data will be collected through Week 56.

Analyses and summaries (including overtime summaries) in general will be carried out during the following study periods when appropriate:

1. From Week 0 through Week 16 (Placebo Controlled Period)
2. From Week 0 through Week 48 (Placebo Controlled and Active Treatment Period)
3. From Week 0 through Week 56

Binary Response Efficacy Endpoints

For binary response efficacy endpoints, treatment comparisons will generally be performed using a Cochran-Mantel-Haenszel (CMH) test stratified by special site (scalp, face, intertriginous, and genital) involvement. The magnitude of the treatment difference will be estimated by the difference in response rates between the guselkumab and placebo groups with a 95% confidence interval (CI) calculated based on Wald statistics (Kim and Won, 2013).

For special site related binary response efficacy endpoints, treatment comparisons will generally be performed using a Chi-squared test. The magnitude of the treatment difference will be estimated by the difference in response rates between the guselkumab and placebo groups with a 95% confidence interval (CI) calculated.

In case of rare events the Fisher's exact test will be used for treatment comparisons as appropriate. The proportion difference between guselkumab group and placebo and the exact confidence interval will be calculated. In these analyses, participants with missing data will be imputed as not achieving the response.

Continuous Efficacy Endpoints

For continuous efficacy endpoints, treatment comparisons will be performed using a Mixed Effects Model for Repeated Measures (MMRM), which relies on the Missing at Random (MAR) assumption for the missing responses. Under the assumption of MAR, the missing data will be accounted for through correlation of repeated measures in the model.

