5.3.3. Analysis Methods

The primary endpoint will be analyzed at Week 16 DBL based on the primary estimand. If a participant experiences ICE of 1 or 2 prior to Week 16, will be treated as non-responders for, IGA score of cleared (0) or minimal (1) response, for the primary analysis. If a participant experiences ICE of 3 then observed value will be used if available.

This primary analysis will include all data collected up to and including Week 16 for all participants in the primary efficacy analysis set. In these primary efficacy analyses, data from all randomized participants will be analyzed according to their assigned treatment group. The primary endpoint at Week 16 will be summarized for each treatment group.

To address the primary objective, a 2-sided ($\alpha=0.05$) CMH chi-squared test stratified by special site (scalp, face, intertriginous, genital) will be used for the primary endpoint.

Statistical analysis for both primary (Estimand 1) and supplementary estimand (Estimand 2) are the same.

The overall Type I error rate will be controlled at the significance level of 0.05. The study will be considered positive if the guselkumab group is significantly different from the placebo. Primary endpoint will be tested at a 2-sided α -level of 0.05.

If the comparison is positive for the primary endpoint, the testing will continue to the major secondary endpoint.

Participants with ICE categories of 1 or 2 before Week 16 will be considered as non-responders at Week 16. Participants with ICE category of 3 before Week 16, observed data will be utilized in the analysis. After accounting for the ICEs for the primary estimand, participants with the missing data of the primary endpoint at Week 16 will be considered as non-responders.

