5.4.1.3.2. Data Handling Rules for Major Secondary Endpoints

5.4.1.3.2.1. Binary Estimands (5,6,7,8,9,10,11,13,14) – Non-responder Imputation (NRI).

Participants who have missing response at Week 16 (after accounting for the intercurrent events) will be considered non-responders at Week 16 (i.e., Non-responder Imputation (NRI)). Similarly, participants who have a missing score at week 16 (after accounting for the intercurrent events) will be considered non-responders for the endpoint at Week 16.

5.4.1.3.2.2. Continuous Estimands (3,4,12)

A missing score (after accounting for the intercurrent events) is not imputed and will be handled through the MMRM assuming missing at random (MAR).

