For participants experiencing ICE's 1 or 2 will be censored. Observed value will be used for the response after the occurrence of ICE 3. For participants experiencing multiple ICEs, an ICE in categories 1 or 2 will supersede an ICE in category 3. Participants who do not achieve the endpoint by Week 16 will be censored for the analysis.

5.4.2.4. Other efficacy endpoints through Week 48

The other efficacy endpoints through Week 48 are listed below. The analyses will be based on full analysis set (FAS). Endpoints after Week 16 through Week 48 will be descriptively summarized by visit. The same missing data handling rules used in Week 16 DBL main analysis will be applied for all endpoints in the final DBL.

1. Change from baseline in BSA \times IGA over time through Week 48
2. The proportion of participants who achieve National Psoriasis Foundation (NPF) target response (i.e., BSA $\leq 1\%$) over time through Week 48
3. The proportion of participants who achieve NPF acceptable response (i.e., BSA $\leq 3\%$) over time through Week 48 among those with baseline BSA $> 3\%$
4. The proportion of participants who achieve PASI 50/75/90/100 over time through Week 48
5. The proportion of participants who achieve IGA 0 over time through Week 48
6. The proportion of participants who achieve IGA 0/1 over time through Week 48
7. Time to achievement of NPF target response (i.e., BSA $\leq 1\%$)
8. Time to achievement of NPF acceptable response (i.e. BSA $\leq 3\%$)

-
9. The proportion of patients who achieve IGA 0/1 at Week 16 and who maintain IGA 0/1 response at Week 48
 10. The proportion of participants achieving palmoplantar IGA (pp-IGA) of clear (0) or almost clear/minimal (1) with at least 2-point improvement over time through Week 48 among randomized participants with a pp-IGA score ≥ 2 at baseline
 11. The proportion of participants achieving pp-IGA of clear (0) over time through Week 48 among randomized participants with palmoplantar psoriasis at baseline
 12. The change from baseline in the Nail Psoriasis Severity Index (NAPSI) over time through Week 48 among randomized participants with nail psoriasis at baseline
 13. The percent improvement from baseline in NAPSI over time through Week 48 among randomized participants with nail psoriasis at baseline
 14. The proportion of participants achieving NAPSI 50/75/90/100 response over time through Week 48 among randomized participants with nail psoriasis at baseline

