 15. The proportion of participants achieving NAPSI 0 over time through Week 48 among randomized participants with nail psoriasis at baseline.
 16. The change from baseline in Psoriatic Arthritis Impact of Disease score (PsAID-12) over time through Week 48
 17. The proportion of participants with a score suggestive of PsA, i.e., ≥ 3 on the Psoriasis Epidemiology Screening Tool (PEST) over time through Week 48 among randomized participants with screening PEST score < 3
 18. The change from baseline in PSSD symptom score over time through Week 48
 19. The proportion of participants who achieve ≥ 4 -point reduction (improvement) in PSSD itch score from baseline over time through Week 48 among participants with a PSSD itch score ≥ 4 at baseline.
 20. The proportion of participants with PSSD Individual Symptom Scale Score = 0 over time through Week 48 among participants with PSSD > 0 at baseline
 21. The change from baseline in individual scale score of PSSD components over time through Week 48.
 22. The proportion of participants who achieve a PSSD individual scale score of 0 over time through Week 48 among randomized participants with scale score ≥ 1
 23. The proportion of participants who achieve a PSSD symptom score = 0 over time through Week 48 among randomized participants with PSSD symptom score ≥ 1

-
24. The proportions of participants who achieve a PSSD symptom score =0 and a PSSD sign score =0 and the proportion of participants who achieve a PSSD individual scale score of 0 for participants with a baseline symptom score, sign score, and each PSSD individual baseline scale score that is ≥ 1 over time through Week 48
 25. The proportion of participants with Dermatology Life Quality Index (DLQI) 0/1 over time through Week 48
 26. The proportion of participants with DLQI 0 over time through Week 48
 27. The change from baseline in PROMIS-29 score over time through Week 48
 28. Change from baseline in Body Surface Area (BSA) affected over time through Week 48
 29. Change from baseline in total Psoriasis Area Severity Index (PASI) score over time through Week 48

5.4.2.5. Definition of other efficacy endpoint (s) through Week 48

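### Carrying non-responder imputation to every Week 48 endpoint counts a missing PEST as not suggestive of psoriatic arthritis, so SAP 5.4.2.4 item 17 is understated

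*SAP*

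**What the plan says.** SAP 5.4.2.4 introduces its list of other efficacy endpoints through Week 48 with one blanket sentence: "The same missing data handling rules used in Week 16 DBL main analysis will be applied for all endpoints in the final DBL". Item 17 of that list is "The proportion of participants with a score suggestive of PsA", defined as PEST of 3 or more, over time through Week 48, among randomized participants whose screening PEST was below 3.

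The rules being carried forward are these:

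- SAP 5.1, binary response endpoints: "In these analyses, participants with missing data will be imputed as not achieving the response".
- SAP 5.3.3, primary endpoint: after intercurrent events are accounted for, "participants with the missing data of the primary endpoint at Week 16 will be considered as non-responders".
- SAP 5.4.1.3.2, major secondary binary endpoints: "participants who have a missing score at week 16 (after accounting for the intercurrent events) will be considered non-responders for the endpoint at Week 16".

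Continuous endpoints are handled differently, by MMRM under missing at random, so within the blanket sentence non-responder imputation (NRI) reaches only the binary endpoints. Item 17 is one of them. SAP 5.4.2.5.3 describes PEST but gives neither a missing-data rule nor a definition of response. It says that a score of 3 or more at screening may indicate undiagnosed PsA.

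**The concern.** NRI is usually chosen because it is conservative: a participant with no data gets the bad outcome. That works only when the counted event is the good outcome. The other binary endpoints in the Week 48 list are favourable (NPF target and acceptable response, PASI, IGA, pp-IGA, NAPSI, PSSD, DLQI). Item 17 is the only one whose counted event is unfavourable. Setting a missing PEST to not achieved gives that participant the good outcome and keeps them in the denominator. The table would then show the proportion known to be positive with all missing values assumed negative, which is not the stated endpoint.

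Some missing data after Week 16 are built into the design. Under Protocol 7.2, a participant who stops study drug at or after Week 16 completes the Week 48 assessments once and then returns only for a final safety visit. The Schedule of Activities has no PEST at Week 56. As missing visits accumulate, the reported proportion is pulled down for a reason unrelated to joint symptoms. If the groups differ in missingness, the group with more missing data looks better.

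**Working it through.** The documents state no PEST rate, dropout rate or missing fraction, so there is no plan figure to reproduce. The inputs below are assumptions, shown as ranges.

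**Inputs**

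- p = true proportion with PEST of 3 or more at a visit (10% for illustration; 5% and 20% also checked)
- d = fraction with missing PEST at that visit (5% to 20%)
- r = risk of PEST of 3 or more in the missing relative to the observed (1 if missingness is unrelated to PEST)

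**Step 1. Missingness unrelated to PEST (r = 1).**

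- Literal NRI reports p(1 − d), so the relative understatement is d.
- Observed cases report p.
- Counting missing as PEST of 3 or more reports p(1 − d) + d. This is also what a programmer would produce by reading non-responder as the unfavourable state.

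For p = 10%:

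| d | Literal NRI | Observed cases | Missing counted as 3 or more |
|---|---|---|---|
| 5% | 9.5% | 10% | 14.5% |
| 10% | 9.0% | 10% | 19.0% |
| 15% | 8.5% | 10% | 23.5% |
| 20% | 8.0% | 10% | 28.0% |

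The absolute shortfall is p × d. It runs from 0.25 points (p = 5%, d = 5%) to 4 points (p = 20%, d = 20%).

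**Step 2. Unequal missingness.** With a true 10% in both groups, 5% missing in one and 15% in the other gives 0.95 × 10% = 9.5% against 0.85 × 10% = 8.5%. That is a 1-point difference created by the rule alone.

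**Step 3. Missingness related to PEST (r above 1).** The risk among the observed is p / ((1 − d) + d·r). NRI reports (1 − d)·p / ((1 − d) + d·r). For p = 10%, d = 15%, r = 2:

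- denominator = 0.85 + 0.30 = 1.15
- literal NRI = 0.085 / 1.15 = 7.4%
- observed cases = 0.10 / 1.15 = 8.7%
- missing counted as 3 or more = 7.4% + 15% = 22.4%

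So NRI is further from the truth than observed cases are, but observed cases are also low. The value r = 2 is illustrative; nothing in the documents supports a particular figure.

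**The case against.** **The direction is not fixed by the text.** SAP 5.1 speaks of response and SAP 5.3.3 of non-responders. PEST of 3 or more is not a response, and SAP 5.4.2.5.3 defines none. A programmer could code missing as the unfavourable state and overstate the proportion. This stands in part. The literal words, "participants with missing data will be imputed as not achieving the response", favour the downward reading, but the possibility of two opposite codings is itself a reason to specify the rule.

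**Little depends on it.** SAP Table 2 places PEST among endpoints summarised for each group, apart from the block that compares groups. SAP 5.4.2.4 makes results after Week 16 descriptive, and both groups are on guselkumab from Week 16. Even with all 200 guselkumab participants, a 10% proportion has a 95% interval of about ±1.96 × √(0.1 × 0.9 / 200) = ±4.2 points, and the PEST subset is smaller. This stands and sets the severity. A reader might infer that the plan is heading for a claim that guselkumab prevents PsA; no passage plans one.

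**Informative missingness is not shown.** A reader might infer that participants who develop joint disease drop out because, under Protocol 6.8.3, "disease-modifying agents such as MTX, sulfasalazine, or IM gold are prohibited during the study". But Protocol 7.1 says only that starting a prohibited therapy leads to notification for possible discontinuation. Those who stop before Week 16 are encouraged to attend through Week 16, and those who stop later complete the Week 48 assessments, which include PEST, at or soon after stopping. The SAP does not say which by-visit slot that last value fills. Risk ratios above 1 therefore remain assumptions.

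**Intercurrent events.** A reader might also infer that an observed PEST of 3 or more is overwritten after a prohibited therapy or a stop for lack of efficacy. SAP 5.4.2.3 words its non-responder rule for events before Week 16, and the sentence in 5.4.2.4 carries forward missing-data rules. Whether the event rule reaches item 17 after Week 16 is uncertain.

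**Conclusion.** The point holds, at low severity. The blanket sentence covers item 17, nothing exempts it, and followed literally it gives missing PEST values the favourable status. If missingness is unrelated to PEST, the by-visit proportion is too low by a relative amount equal to the missing fraction. The understatement is larger if those missing are at higher risk. The size rests entirely on assumed missing fractions and rates.

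The documents do not support saying that the bias must be downward however the rule is programmed, that dropouts are known to have more joint symptoms, or that a prevention claim is planned. The primary and major secondary results are untouched.

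**What to change.** Add to SAP 5.4.2.4:

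- NRI does not apply to item 17.
- At each visit, the proportion with PEST of 3 or more is calculated among participants with an observed PEST, showing the number observed and the number missing by group.
- A sensitivity summary counts missing PEST as 3 or more, as an upper bound.
- Observed PEST values are used regardless of intercurrent events.

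A cumulative proportion with PEST of 3 or more at any post-baseline visit would be a new, optional summary and is not needed for this fix.

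The cost is a few SAP sentences, one changed table and one added bounding summary, with no new data. Denominators will vary by visit. Observed-case results may still be somewhat biased if missingness is related to joint symptoms, which is why the number missing and the bound should be shown alongside.

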
Other Objectives To evaluate the efficacy of additional clinical and patient-reported outcomes
	
Other Endpoints - Psoriasis Efficacy
 
The following endpoints will compare the guselkumab group with the placebo group:
 
 
• Change from baseline in BSA × IGA through Week 16
 
 
The following endpoints relate to the guselkumab group only:
 
 
• Change from baseline in BSA × IGA over time through Week 48
 
• The proportion of participants who achieve National Psoriasis Foundation (NPF) target response (i.e., BSA ≤1%) over time through Week 48
 
• The proportion of participants who achieve NPF acceptable response (i.e., BSA ≤3%) over time through Week 48 among those with baseline BSA >3%
 
• The proportion of participants who achieve PASI 75/90/100 over time through Week 48
 
• The proportion of participants who achieve IGA 0 over time through Week 48
 
• The proportion of participants who achieve IGA 0/1 over time through Week 48
 
• Median time to achievement of NPF target response (i.e., BSA ≤1%)
 
• Median time to achievement of NPF acceptable response (i.e., BSA ≤3%)
 
• The proportion of patients who achieve IGA 0/1 at Week 16 and who maintain IGA 0/1 response at Week 48
 
 
Other Endpoints – Special Site Efficacy
 
The following endpoints will compare the guselkumab group with the placebo group:
 
Scalp
 
 
• Time to complete scalp psoriasis clearance (ss-IGA = 0) among randomized participants with scalp psoriasis at baseline
 
• Proportion of participants with complete scalp psoriasis clearance (ss-IGA = 0) over time among randomized participants with scalp psoriasis at baseline over time through Week 16
 
• Proportion of participants who achieve an ss-IGA score of absence of disease (0) or very mild disease (1) with at least 2-grade improvement from baseline at Week 16 among randomized participants with an ss-IGA score ≥2 at baseline
 
 
Genital
 
 
• Time to complete genital psoriasis clearance (sPGA-G = 0) among randomized participants with genital psoriasis at baseline
 

--	---

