### Participant and Disease Characteristics

2. Have a diagnosis of plaque psoriasis (with or without PsA) for at least 6 months before the first administration of study intervention.
3. All participants must meet the following disease severity criteria at screening and at baseline:
  - a) Overall IGA 3 (moderate) plaque psoriasis  
AND
  - b) BSA 2-15% with at least 1 plaque outside of special sites  
AND
  - c) Involvement of at least 1 special site with at least moderate severity. Qualifying sites include scalp with ss-IGA  $\geq 3$ , face with f-IGA  $\geq 3$ , intertriginous with i-IGA  $\geq 3$ , or genital with sPGA-G  $\geq 3$ .
4. Be inadequately controlled with or intolerant of at least 1 prior topical therapy (including, but not limited to, corticosteroids, retinoids, vitamin D, or vitamin D/steroid and retinoid/steroid combinations, tacrolimus, pimecrolimus, anthralin/dithranol, coal tar preparations, tapinarof, roflumilast, etc.) for the treatment of psoriasis at both screening and baseline.
5. Be a candidate for phototherapy or systemic treatment for psoriasis (either naïve or history of previous treatment; see Exclusion Criterion 6 for washout of prior treatments).
6. Be considered, in the opinion of the investigator, suitable candidates for guselkumab therapy according to their country's approved product labeling.

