reported outcomes	
group
 
 1. Change from baseline in BSA x IGA through Week 16 
The following endpoints relate to guselkumab group only
 
 2. Change from baseline in BSA x IGA over time through Week 48 3. The proportion of participants who achieve NPF target response (i.e., BSA\leq1%) over time through Week 48 4. The proportion of participants who achieve NPF acceptable response (i.e., BSA \leq3% or BSA75) over time through Week 48 among those with baseline BSA >3% 5. The proportion of participants who achieve PASI 50/75/90/100 over time through Week 48 6. The proportion of participants who achieve IGA 0 over time through Week 48 7. The proportion of participants who achieve IGA 0/1 over time through Week 48 8. Time to achievement of NPF target response (i.e., BSA \leq1%) through Week 48 9. Time to achievement of NPF acceptable response (i.e., BSA\leq3% or BSA75) through Week 48 10. The proportion of IGA 0/1 Week 16 responders who maintain IGA 0/1 response at Week 48 11. Change in BSA over time through Week 48 12. Change in PASI over time through Week 48 
Other Endpoints – Special Site Efficacy
 
The following endpoints will compare the guselkumab with the placebo group
 
Scalp
 
 13. Time to complete scalp psoriasis clearance (ss-IGA = 0) through Week 48, among randomized participants with scalp psoriasis at baseline 14. Proportion of participants with complete scalp psoriasis clearance (ss-IGA = 0) over time among randomized participants with scalp psoriasis at baseline over time through Week 16 15. Proportion of participants who achieve an ss-IGA score of absence of disease (0) or very mild disease (1) with at least 2-grade improvement from baseline at Week 16 among randomized participants with an ss-IGA score \geq2 at baseline 
Genital
 
 16. Time to complete genital psoriasis clearance (sPGA-G = 0) through Week 48, among randomized participants with genital psoriasis at baseline 17. Proportion of participants with complete genital psoriasis clearance (sPGA-G = 0) among randomized participants with genital psoriasis at baseline over time through Week 16 18. Proportion of participants who achieve an sPGA-G score clear (0) or minimal (1) with at least 2-grade improvement from baseline at Week 16 among randomized participants with an sPGA-G score \geq2 at baseline

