4. POPULATIONS (ANALYSIS SETS) FOR ANALYSIS

The analysis sets and the descriptions are defined below in [Table 6](#).

Table 6: Analysis Sets

Analysis Sets	Description
Enrolled	All participants who signed the informed consent form (ICF). This analysis set will be used for summarizing the overall study completion/withdrawal information.

Table 6: Analysis Sets

Analysis Sets	Description
Full Analysis Set (FAS) -Efficacy Analysis Set	All participants who were randomized in the study. This analysis set will be used for the efficacy analyses.

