The explanatory variables of the MMRM model will include treatment group, visit, baseline efficacy endpoint score, special site (scalp, face, intertriginous, and genital) an interaction term of visit with treatment group, and an interaction term of visit with baseline efficacy endpoint score. An unrestricted (UN) variance-covariance matrix for repeated measures within a participant will be used. If the model with unstructured covariance structure does not converge, alternative covariance structures will be tried in the following order, with the first structure that converges being used in the analysis: heterogeneous Toeplitz (TOEPH) or autoregressive of order 1 (AR (1)).

The baseline measurement is defined as the closest measurement taken prior to or at the time of the first study agent administration date unless otherwise specified.

The change from baseline is calculated as the post baseline value minus the baseline value.

Change from baseline= Post Baseline Value – Baseline Value

Percent Change from Baseline= ((Post Baseline Value-Baseline Value)/Baseline Value) *100

If a higher score indicates more severe disease in efficacy assessments, then a negative change indicates an improvement, and a positive change indicates worsening.

The treatment difference between a guselkumab group and the placebo group will be estimated by the difference in the LS means. The 95% CIs for the differences in LS means and p-values will be calculated.

Time to an Event Efficacy Endpoints

Survival analysis techniques such as life-table estimates will be calculated for time to event efficacy endpoints for the 2 treatment groups. The log-rank test stratified by special site (scalp, face, intertriginous, and genital) will be used to compare the time to event efficacy endpoints. For the special site related endpoints, stratification will not be used for the log rank test to compare the time to event efficacy endpoints.

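### Time to NPF acceptable response (BSA 3% or less) has no baseline BSA restriction, so participants who enter at BSA 2-3% count as early responders without improving

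*SAP*

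**What the plan says.** Protocol Section 5.1, Inclusion Criterion 3, requires "BSA 2-15% with at least 1 plaque outside of special sites" at screening and at baseline, so a participant with BSA of 2% or 3% is eligible.

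The NPF acceptable response appears in two forms:

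- **Proportion.** SAP Section 5.4.2.4, item 3, takes the proportion with BSA of 3% or less "over time through Week 48 among those with baseline BSA" above 3%. SAP Table 2 (item 4) and protocol Section 3 carry the same restriction.
- **Time to event.** SAP Section 5.4.2.4, item 8, is "Time to achievement of NPF acceptable response", with BSA of 3% or less as the event and no baseline condition. SAP Table 2, item 9, has none either, and protocol Section 3 lists "Median time to achievement of NPF acceptable response", again without one.

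The Week 48 endpoints are analysed in the Full Analysis Set, which SAP Section 4 defines as "All participants who were randomized in the study. This analysis set will be used for the efficacy analyses". On method, SAP Section 5.1 says "Survival analysis techniques such as life-table estimates will be calculated for time to event efficacy endpoints for the 2 treatment groups". The censoring rules in SAP Section 5.4.2.3 deal with intercurrent events 1 and 2 and with participants who do not reach the endpoint. Nothing addresses participants who already meet it at baseline.

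The definition also varies. SAP Table 2 ends the time endpoint with "or BSA75) through Week 48", so the response there is BSA of 3% or less, or BSA75. SAP Section 5.4.2.4 and the protocol use the 3% threshold alone.

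**The concern.** A time-to-event analysis should start with people who can still have the event. Here a participant enrolled at BSA 2% satisfies the event at Week 0, or at the latest is likely to do so at the first post-baseline visit (Week 4), whatever the drug does. Someone who worsened from 2% to 3% would still be a responder.

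The plan recognises the issue elsewhere. The companion proportion is restricted, the special-site clearance times are limited to participants with disease at that site at baseline, and several PSSD endpoints exclude those already at zero. Time to NPF target response (BSA of 1% or less) is safe, because entry requires at least 2%. The gap is specific to this endpoint.

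At stake is the reported speed of response in a low-BSA trial, where a fixed 3% threshold is especially likely to be met at entry. A median that partly reflects eligibility would make guselkumab look faster than it is. It would also use a different denominator from the proportion reported beside it.

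**Working it through.** The plan states no sample size, event rate or expected median for this endpoint, so there is no figure to reproduce.

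**Inputs from the documents**
- Eligible BSA: 2% to 15% (protocol Section 5.1).
- Event: BSA of 3% or less; analysis set: all randomized (SAP Sections 5.4.2.4 and 4).
- About 200 participants randomized to guselkumab (SAP Section 3).
- BSA assessed at Week 0 and every 4 weeks through Week 48 (protocol Section 1.3).

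**Assumed inputs (not in the documents)**
- f, the share with baseline BSA of 3% or less: 5% to 30%. For orientation only, a uniform spread over 2-15% would give 1/13 = 7.7%.
- F(t), cumulative response among those starting above 3%.

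**Formula.** If participants already at target count from the start, or from Week 4, the apparent cumulative response at any later visit is f + (1 - f) x F(t). The apparent median is reached when F(t) = (0.5 - f)/(1 - f), which is below 50% for every f above 0.

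**Illustration 1: assumed F of 20/40/55/65% at Weeks 4/8/12/16**
- Week 4, f = 10%: 0.10 + 0.90 x 0.20 = 28%.
- Week 4, f = 20%: 0.20 + 0.80 x 0.20 = 36%.
- Week 4, f = 30%: 0.30 + 0.70 x 0.20 = 44%.
- The true visit-based median is Week 12. It moves to Week 8 once f + 0.40(1 - f) reaches 0.5, so f = 0.1/0.6 = 16.7%, or about 33 of 200 participants.

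That threshold depends on the assumed Week 8 response p, through (0.5 - p)/(1 - p):
- p = 30%: 0.20/0.70 = 29%.
- p = 40%: 17%.
- p = 45%: 0.05/0.55 = 9%.

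**Illustration 2: assumed exponential response, continuous-time median in weeks**

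| True median (BSA above 3%) | f = 5% | f = 10% | f = 20% | f = 30% |
|---|---|---|---|---|
| 8 | 7.4 | 6.8 | 5.4 | 3.9 |
| 12 | 11.1 | 10.2 | 8.1 | 5.8 |
| 16 | 14.8 | 13.6 | 10.9 | 7.8 |

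This is a shortening of about 7%, 15%, 32% and 51%. The response needed among true candidates to reach the median falls from 50% to 47.4%, 44.4%, 37.5% and 28.6%.

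If the median is read at the 4-weekly visits, the 12-week case shows no shift up to f = 20% and moves to Week 8 at f = 30%. The Week 4 response still rises, from 20.6% to 28.6% at f = 10%.

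**Definition mismatch.** If BSA75 means at least a 75% reduction in BSA (the documents do not define it), it adds responders only when 0.25 x baseline exceeds 3, that is, when baseline BSA is above 12%. Because the two criteria are joined by *or*, it does nothing for participants who start at 2-3%.

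**The case against.** The strongest reply concerns weight. This is one of 47 numbered other efficacy endpoints in SAP Table 2. It is listed for the guselkumab group only, is summarised descriptively after Week 16 and has no multiplicity control. No success criterion depends on it. That is correct and limits the importance of the point.

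A second reply is that the SAP does not say whether a Week 0 value counts as an event, or whether achievement implies a change of state, and that a programmer might carry over the restriction in item 3. The dating rule is indeed unstated, but the direction of the bias is the same under Week 0 or Week 4 dating. Carrying over the restriction would depart from the written analysis set.

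A third is that the size rests on invented curves and an unknown f. This stands. The 17% threshold comes from one assumed Week 8 response and ranges from 9% to 29% as that response varies from 45% to 30%; a small f may leave a visit-based median where it was. The omission and the direction of its effect are firm; the size is not.

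**Conclusion.** The concern holds. Followed as written, SAP Section 5.4.2.4 item 8 counts participants enrolled at BSA 2-3% as responders without improvement, which raises the early curve and leaves the median shorter or unchanged. Under the assumed curves, a 10-30% share at or below 3% adds 8 to 24 percentage points to a 20% Week 4 response and takes about 15% to 51% off a continuous-time median. The share, the response curve and the exponential shape are assumptions; the actual effect can be known only from the baseline BSA distribution.

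The primary and major secondary inference is untouched. The inconsistent definition of acceptable response is a separate, smaller fault that affects both the time and proportion versions.

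**What to change.** - In SAP Table 2 item 9 and Section 5.4.2.4 item 8, restrict the time to NPF acceptable response to participants with baseline BSA above 3%, matching the proportion endpoint. Protocol Section 3 has the same gap, so correct it at the next amendment or record the SAP wording as a clarification.
- Choose one definition of acceptable response and use it for both the time and proportion versions in Table 2 and Section 5.4.2.4. If BSA75 is kept, define it.
- State that events are dated from the first post-baseline assessment meeting the criterion.
- Report how many participants are excluded because their baseline BSA is 3% or less.

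The cost is a few lines of SAP wording and a somewhat smaller set for one descriptive analysis. No new data or procedures are needed.
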